7. If their sexual partners can become pregnant, male participants should use a method of contraception during study participation and for six months after the last administration of the experimental drug. *
8. The study participant is able and willing to comply with the requirements of this clinical trial.

Exclusion Criteria

A study participant will not be eligible for inclusion in this clinical trial if any of the following criteria apply:

1. The subject is unable to provide informed consent or to comply with study requirements.
2. A study participant has currently been diagnosed with active COVID-19 disease, defined as ongoing symptoms related to acute infection (such as fever or chills, cough, shortness of breath, or difficulty breathing, among other symptoms), and evidence of a positive RT-PCR SARS- CoV-2.
3. The subject is unwilling to agree to the use of acceptable methods of contraception * throughout the study and for six months after the last dose of the investigational product.
4. Pregnancy, lactation. Women of childbearing age who are not pregnant but do not take adequate contraceptive measures. *
5. The study participant has a history of addiction or dependency, or he or she is currently abusing or using substances.
6. Study participant has any active malignancy, including but not limited to evidence of cutaneous basal, squamous cell carcinoma, or melanoma.
7. The study participant has one or more significant concurrent medical conditions (verified by medical records), including the following:

- Diabetes Mellitus (DM)	Poorly controlled diabetes mellitus (PCDM), defined as a history of deficient standard of care treatment or pre-prandial glucose >130mg/dl during screening visit or post-prandial glucose >200mg/dl.
- Chronic kidney disease (CKD)	Medical History of Chronic kidney disease (CKD) diagnosis or screening results of eGFR < 59mL/min/1.73m ² . Subjects with any form of kidney dialysis will be excluded from participation in this clinical trial.
- Heart Failure	Presence of New York Heart Association (NYHA) Class III/IV heart failure during the screening visit.
- Myocardial Infarction	Medical history of myocardial infarction in any of the different types, such as ST-elevation myocardial infarction (STEMI) or non-ST-elevated myocardial infarction (NSTEMI), coronary spasm, or unstable angina.

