- High Blood Pressure	Medical history of uncontrolled high blood pressure is defined as a deficient standard of care treatment or blood pressure > 140/90 mm/Hg during the screening visit in a patient taking anti-hypertensive treatment. At screening, all patients must have a blood pressure < 140/90 mm/Hg.
- Other diseases	Medical history of inherited thrombophilias, cancer of the lung, brain, lymphatic, gynecologic system (ovary or uterus), or gastrointestinal tract (like pancreas or stomach).
- Other conditions	Lower extremity paralysis due to spinal cord injury, fracture of the pelvis, hips or femur or recent major general surgery (within 12 months before the Screening).

8. Study participant has received any stem cell treatment within 12 months before the first dose of the investigational product other than stem cells produced by Hope Biosciences.
9. The study participant has received an experimental drug within 12 months before the first dose of the investigational product. (Except for COVID-19 vaccinations)
10. Study participant has a laboratory abnormality during screening, including the following:
 - White blood cell count WBC \leq 3.0 K/UL and \geq 12.0 K/UL
 - Platelet count \leq 80 K/UL and or \geq 450 K/UL
 - Absolute neutrophil count \leq 1.50 K/UL and or \geq 7.50 K/UL
 - Alanine aminotransferase (ALT) of > 75 U/L
 - Aspartate aminotransferase (AST) of > 75 U/L
 - Hemoglobin (Hgb) <11 G/DL or >18 G/DL
 - Hematocrit (HCT) <33% or >54 %
 - Mean corpuscular volume (MCV) < 75 FL or >100 FL
 - Mean corpuscular hemoglobin (MCH) <23 PG or >36 PG
 - Mean corpuscular hemoglobin concentration (MCHC) <30 G/DL or > 37gG/DL
 - Red cell distribution width (RDW) < 10% or >14%
 - Abnormal laboratory results considered clinically significant by the principal investigator will exclude patients from participation in this investigation. See annexes for laboratory normal values.

11. The study participant has any known ongoing infection, including but not limited to TB, CMV, EBV, HSV, VZV, hepatitis virus, toxoplasmosis, HIV, syphilis infections, hepatitis B surface antigen-positive, or hepatitis C PCR positivity.
12. The study participant is unlikely to complete the study or adhere to the study procedures.
13. The study participant has a previously diagnosed psychiatric condition that may affect self-assessments in the investigator's opinion.

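### Exclusion 10 joins the two white-cell limits with *and*, which no count can satisfy, so read literally that row excludes nobody

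*Protocol*

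**What the plan says.** The Protocol's Exclusion Criteria open with the rule that one criterion is enough to exclude: "A study participant will not be eligible for inclusion in this clinical trial if any of the following criteria apply". Item 10 begins "Study participant has a laboratory abnormality during screening, including the following" and then gives a row for each test. The white-cell row is "White blood cell count WBC \leq 3.0 K/UL and \geq 12.0 K/UL".

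The next two rows are "Platelet count \leq 80 K/UL and or \geq 450 K/UL" and "Absolute neutrophil count \leq 1.50 K/UL and or \geq 7.50 K/UL". From there the two-limit rows use a plain *or*, for example "Hemoglobin (Hgb) <11 G/DL or >18 G/DL". Hematocrit, MCV, MCH, MCHC and RDW follow the same pattern. ALT and AST have one limit each.

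The item closes with a general provision: "Abnormal laboratory results considered clinically significant by the principal investigator will exclude patients from participation in this investigation".

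Neither the Protocol nor the SAP restates the white-cell limits or corrects the connective anywhere else.

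**The concern.** This is an operative eligibility rule. Under Clinical Trial Population a participant must meet none of the exclusion criteria, and under Investigational Product Assignment only eligible subjects are randomized. If the row is copied as it stands into an eligibility checklist, a candidate whose white count the Protocol evidently meant to exclude can be ticked as eligible, with no deviation on record. If staff silently read *or*, they apply a sensible rule that the document does not state, and a later audit cannot tell which rule governed.

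The row bears on safety. Infections are an adverse event of special interest, and changes in laboratory values are listed under Primary Endpoints. What is at stake is who enters and whether entry is decided by a stated limit or by judgement. The treatment comparison is not at issue.

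**Working it through.** The plan gives no figure to reproduce. The check is one of logic, followed by a sizing of what the neutrophil row still catches.

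**Inputs** (all from the Protocol)
- White-cell limits: 3.0 and 12.0 K/UL (exclusion 10).
- Absolute neutrophil limits: 1.50 and 7.50 K/UL (exclusion 10).
- Reference ranges: white cells 3.5-11.0 K/UL; neutrophil share 40-75%; absolute lymphocytes 1.00-4.00, monocytes 0.20-1.00, eosinophils 0.00-0.50, basophils 0.00-0.20 K/UL (Clinical Safety Laboratory Parameters).

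**Step 1: the white-cell row.** The set of counts with WBC ≤ 3.0 and WBC ≥ 12.0 is empty. On a grid from 0 to 50 K/UL in steps of 0.01, 0 of 5001 values meet it. Joined by *or*, the row excludes every value at or below 3.0 or at or above 12.0, and counts strictly between them pass.

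**Step 2: the other two-limit rows.** *And or* is an inclusive *or*. For ranges that do not overlap it gives the same result as *or*, so the platelet and neutrophil rows work. The six later rows use *or*. Eight of nine rows are therefore sound.

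**Step 3: what the neutrophil row still catches.** Absolute neutrophils = WBC × neutrophil share.
- At WBC 3.0 the row excludes only if the share is at most 1.50 / 3.0 = 50%.
- At WBC 12.0 it excludes only if the share is at least 7.50 / 12.0 = 62.5%.
- Over shares of 40-75%, it always excludes low counts when WBC × 0.75 ≤ 1.50, that is WBC ≤ 2.0.
- Over the same shares, it always excludes high counts when WBC × 0.40 ≥ 7.50, that is WBC ≥ 18.75.

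Counts above 2.0 up to 3.0, and from 12.0 to below 18.75, can therefore pass. Examples:
- WBC 2.5 at 65%: 2.5 × 0.65 = 1.625.
- WBC 13.0 at 50%: 13.0 × 0.50 = 6.5.
- WBC 15.0 at 45%: 15.0 × 0.45 = 6.75.

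All three results lie strictly between 1.50 and 7.50.

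**Step 4: would these people be noticed?** Every count in the two windows is outside 3.5-11.0, so at least one result is flagged. The differential often adds a second flag.
- The upper limits for the other four cell types sum to 4.00 + 1.00 + 0.50 + 0.20 = 5.70. WBC 13.0 at 50% leaves 6.5 other cells and WBC 15.0 at 45% leaves 8.25, so in each case at least one of those types must be high.
- WBC 2.5 at 65% leaves 0.875, so lymphocytes must be below 1.00.
- The second flag is not certain nearer the limits. Below 7.50 + 5.70 = 13.20, and above 1.50 + 1.00 + 0.20 = 2.70, every absolute differential count can be in range while the white count itself is not.

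**The case against.** The strongest case against is that *and* need not be a Boolean operator here. The lead-in introduces a list of abnormalities, so the row can be read as naming two abnormal ranges, either of which excludes. The literal reading makes the row meaningless, the neighbouring rows show what was meant, and nothing in the documents suggests that anyone would apply the impossible version. This stands as an argument about effect: a site would probably read two separate ranges. It does not make the wording right, because this row alone lacks an *or* and no other text supplies one.

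A second argument is that item 10 is open-ended and that its closing bullet makes exclusion mandatory once a result is judged clinically important. That is true, and it narrows the gap. It does not replace the limit, because whether the bullet applies is a judgement. Nor can the lead-in mean that any out-of-range value excludes. ALT excludes above 75 U/L although its reference range ends at 40, and platelets exclude at 80 K/UL or below although theirs starts at 130. Those limits would serve no purpose on that reading.

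A third argument is that infection is covered elsewhere: active COVID-19 (item 2), known ongoing infection (item 11), recently treated systemic infection (item 14), pneumonia (item 20) and general unsuitability (item 16). This also stands and weakens the safety argument, though none of these items sets a limit on an unexplained white count.

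A reader might also infer that the list runs on three conflicting logics and that the platelet and neutrophil rows are faulty too. The text does not support that, since *and or* and *or* give the same result for these ranges.

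**Conclusion.** The point holds for one row. Read literally, the white-cell row of exclusion 10 excludes nobody, and no other text corrects it. It is most likely a drafting slip, and it is minor.

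Its reach is bounded. White counts above 2.0 up to 3.0, and from 12.0 to below 18.75 K/UL, can pass every stated numeric white-cell limit, and exclusion then depends on the investigator. These bounds assume a neutrophil share within 40-75%; shares outside that range would widen them. The documents do not give the proportion of screened candidates with such counts. It is probably small.

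A reader might infer that the Protocol has no working white-cell exclusion, or that people with abnormal counts will be enrolled unnoticed. Neither follows. The neutrophil row still operates, every count in the two windows falls outside the reference range, and the closing bullet can exclude. The eligibility form is not among the documents, so whether it repeats the wording is unknown. Sample size, power, significance level and analysis are unaffected, and nothing here points to bias between the arms.

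**What to change.** In exclusion 10, reconcile the connective in the white-cell row with the other two-limit rows, leaving both thresholds as they are. Confirm that the eligibility case report form and any screening checklist carry the same logic. Changing *and or* to *or* in the platelet and neutrophil rows would make the list uniform, but that is cosmetic.

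The cost is one word in the next Protocol amendment and a check of the form. If the site already reads the row as two separate ranges, screening does not change. If it does not, the result is at most a few more screen failures, among people the limits were evidently meant to exclude.

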- Visit 8 – End of Study, during this final visit (approximately 26 weeks after Week 0), an entire group of study assessments will be performed to evaluate the safety and efficacy of HB-adMSCs (allogeneic) or Placebo administrations.

Clinical assessments of disease activity will take place during the following visits:

- Visit 1 – Screening
- Visit 2 – Infusion 1 → **(Baseline)**
- Visit 3 – Infusion 2
- Visit 4 – Infusion 3
- Visit 5 – Infusion 4
- Visit 6 – Follow Up 1
- Visit 7 – Follow Up 2
- Visit 8 – End of Study

Blood samples for safety evaluations will be obtained at the following visits:

- Visit 1 – Screening. After informed consent has been obtained, laboratory samples will be drawn by venipuncture; the findings of the lab tests will be used to determine whether the individual is eligible for the research.
- Visit 2 – Infusion 1 **(Baseline)**: safety laboratory samples will be drawn by venipuncture to establish a baseline for comparison with the laboratory results obtained in subsequent visits.
- Visit 5 – Infusion 4: safety laboratory samples should be collected by venipuncture during this visit.
- Visit 8 – End of Study: safety laboratory samples should be collected by venipuncture during this visit.

Suppose a study participant receives at least one dose of the experimental drug and decides to withdraw consent after that. In that case, investigators should conduct a safety follow-up visit with this subject's approval to comply with the Sponsor's standard operating procedures.
--

Withdrawal Criteria

In different situations, a study subject may withdraw from the study before the planned completion of the visits. One of these situations is mentioned below,

1. Voluntary withdrawal: the subject doesn't want to continue receiving the investigational product.

The principal investigator and designated staff must record the reason for the subject's withdrawal on the case report forms, specifically in the Early Termination Visit or a Note to File Form.

Study participants discontinued from the clinical trial who received at least one infusion (HBadMSCs - allogeneic or placebo) will be invited to a Safety Follow-up visit.

Any withdrawal must be documented in the source documents and electronic case report forms. If the reason for the discontinuation is an adverse event or serious adverse event, the event must be followed until resolution by the principal investigator.

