Clinical evaluators (data analysts and physicians) will be trained to maintain blinding to treatment as best as possible to minimize assessment bias. “Best as possible” means that blinding will be held unless an adverse event or serious adverse event occurs that requires unblinding the physician, which is determined by the DSMB.

Training includes a review of the process of blinding, describing who will be responsible for assigning products for the appropriate group, labels that will be used to identify subjects but not treatment group, and the process that should be followed if an adverse event occurs, triggering a review by medical monitor or DSMB.

Prior and Concomitant Medications

Concurrent and prior medications (up to one week before the screening visit) should be recorded in the subject’s medical history at the screening visit. This list of concomitant medications may be updated, if necessary, at the subsequent visits.

It is essential to ask the subject about the start and end date of the current and prior medications. If the subject does not remember the specific date or month, it is recommended to include the approximate year to estimate how long the patient has been taking the medication.

Trial Procedures

The trial includes an up to 28 days screening period, a 10-week Treatment Period, and a 26-week Safety Follow-up Period. All periods are associated with evaluations and procedures that must be performed at specific time points, as represented in Table 1 Schedule of Assessments.

Trial Schedule of Assessments.

Table 1 Schedule of Assessments.

	Visit 1	Randomization	Visit 2	Visit 3	Visit 4	Visit 5	Visit 6	Visit 7	Visit 8
Visit Names	Screening		INF 1 Baseline	INF 2	INF 3	INF 4	Follow Up 1 Phone Call	Follow Up 2 Phone Call	EOS
Window Period	Up to 28 days		± 7 days	± 7 days	± 7 days	± 7 days	± 7 days	± 7 days	± 7 days
Visit Weeks	N/A		0	2	6	10	14	20	26
Informed Consent	X								
Demographics	X								
Medical History	X		X	X	X	X	X	X	X
Concomitant Medications	X		X	X	X	X	X	X	X
Eligibility Criteria	X								
Vital Signs	X		X	X	X	X			X
Weight	X		X	X	X	X			X
Height	X								
Laboratory Samples	X		X			X			X
Physical Examination	X		X	X	X	X			X
Visual Analog Scale of Symptoms	X		X	X	X	X			X
Fatigue Scale	X		X	X	X	X			X
SF-36			X			X			X
PHQ-9	X		X	X	X	X			X
Pre-medications			X	X	X	X			
Study Treatments Administration			X	X	X	X			
24 hours Telephone Encounter			X	X	X	X			
AE and SAE assessments			X	X	X	X	X	X	X

- INF indicates Infusion in visit names.

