- Laboratory samples (CBC- complete blood count, CMP- comprehensive metabolic panel & Coagulation Panel)
- Short Form 36 Health Survey Questionnaire (SF-36)
- PHQ 9 -Patient Health Questionnaire
- Adverse Events (AE) and Serious Adverse Events (SAE)

Study Visits 1 to 6.

Visit 1 – Screening.

At the Screening Visit (Visit 1), study participants' information will be collected by the study's delegated personnel to evaluate trial eligibility. The following information is required to determine eligibility:

1. Signing Informed Consent Form (before any trial-related activities).
2. Collection of demographic information, such as age, race, ethnicity, date of birth, gender, and relevant medical and surgical history.
3. Collection of Medical History and concomitant medications, including relevant information about study participants' past and present health.
4. Inclusion and Exclusion criteria evaluation.
5. Measurement of vital signs includes respiratory rate (breaths per minute), body temperature (F), blood pressure (mmHg), pulse rate (beats per minute), oxygen saturation (%), weight (lb. or kg) and height measurement (inches or cm).
6. Collection of laboratory samples - Comprehensive Metabolic Panel (CMP), Complete Blood Count (CBC), Coagulation Panel, and Urine pregnancy test if female of childbearing potential.
7. Physical examination by Principal Investigator.
8. Completion of patient questionnaire including Visual Analog Scale of Symptoms, Fatigue scale and PHQ-9.

Within 28 days of the Visit 1 - Screening, the principal investigator must decide the participant's eligibility. Once the principal investigator has confirmed the subject's eligibility, the randomization process will be conducted.

Visit 2 – Infusion 1 (Baseline)

The following procedures are required during this visit:

1. Update medical history and concomitant medications if any change occurred since the last visit.
2. Measure vital signs, including respiratory rate (breaths per minute), body temperature (F), blood pressure (mm Hg), pulse rate (beats per minute), oxygen saturation (%), and weight measurement (lb. or kg).
3. The following baseline vital signs must be met for the infusion to proceed:
 - Pulse rate: ≥ 50 bpm and ≤ 100 bpm
 - SBP: ≤ 160 mmHg and ≥ 95 mmHg **
 - DBP: ≤ 95 mmHg and ≥ 50 mmHg
 - Respiratory rate: ≥ 10 bpm and ≤ 20 bpm
 - Pulse oximeter: $\geq 94\%$ O₂ saturation
4. Physical examination by Principal Investigator.

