The FAS is a ten-item scale that assesses the symptoms of chronic fatigue in an individual. The FAS considers fatigue as a unidimensional concept rather than a collection of variables that may be measured separately. Additionally, to guarantee that the scale would assess all elements of fatigue, the scale's developers included questions that represented both physical and mental symptoms of the disease (Michielsen et al., 2004).

Short Form Questionnaire – 36

The SF-36 is a multi-purpose survey intended to collect adult patients' views of their health and well-being. In all, there are 36 questions on the SF-36, which are organized into eight dimensions: physical functioning, physical and emotional limitations, social functioning, physiological discomfort, general and mental health. It is a more public health measure than targeted at a particular age group, illness, or treatment group. This questionnaire may be given in various situations (e.g., primary care, community clinics, specialty care serving patients with chronic conditions). It has been extensively utilized and proved helpful in multiple studies of general and populations throughout the years, including evaluating the relative burden of illnesses and differentiating the health benefits provided by a range of various therapies (National Center for Interprofessional Practice and Education, 2016).

Physical Examinations

The principal investigator or delegated sub-investigator will perform a complete physical examination. This exam will include general appearance, head, eyes, ear, nose, and throat (HEENT), neck, cardiovascular, thorax/lungs, abdomen, genitourinary, musculoskeletal, lymph nodes, skin, neurological and mental status examination, height (at Screening only), and body weight at Visits 1, 2, 3, 4, 5, 6, 7 and 8.

The principal investigator or delegated sub-investigator will evaluate the clinical significance of abnormal findings identified during physical examinations. Pre-existing conditions diagnosed through assessments and examinations at the screening visit or during the screening period are not adverse events but are recorded as medical history. If any clinically significant abnormal findings are

discovered after informed consent or any pre-existing conditions worsen during the trial, these must be recorded as adverse events.

Vital Signs

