All adverse events that do not meet any of the criteria for serious should be regarded as *nonserious adverse events*.

Adverse Event Reporting Period

The study period during which adverse events must be reported is typically defined as the period from the initiation of any study procedures to the end of the study treatment follow-up. For this study, treatment follow-up is described as approximately 16 weeks following the last administration of study treatment.

Stopping Rules

Infusion Stopping Rules

Study treatment infusion will be stopped if a least one of the following events occurs:

1. Allergic reaction as evidenced by severe dyspnea (defined as intense tightening of the chest, air hunger, breathlessness or feeling of suffocation), bronchospasm (defined as coughing, wheezing, difficulty breathing) or hypoxia (defined as pulse oximeter reading of less than 90%) after the product has been administered intravenously.
2. Hypersensitivity reactions such as rash, urticaria, itching, angioedema, nausea, vomiting, hypotension, or any evidence of anaphylaxis.
3. The patient verbally declines the treatment at any moment prior, or during the infusion.
4. Any febrile reaction will be an indicator for pausing the infusion for further evaluation.
5. Malignant Systolic blood pressure (SBP) greater than 170 and/or diastolic blood pressure greater than 100. SBP less than 80mm/Hg and/or DBP less than 40mm/Hg. *
6. Sudden Severe Hypotension (40 mm/Hg drop from infusion starting baseline) or systolic blood pressure <80mmHg.
7. Respiratory distress defined as having an acute sudden onset of shortness of breath or increased work of breathing, SaO₂ less than 90% or a respiratory rate >22 or < 10 breaths per minute. Any increased oxygen support that could indicate imminent respiratory failure.
8. Sudden increase or decrease in pulse rate of 30 bpm or more from infusion starting baseline or an absolute tachycardia of greater than 140 bpm or absolute bradycardia less than 45 bpm.
9. Change in neurologic status from infusion starting baseline including alertness.
10. The Principal Investigator may stop the infusion at any time, based upon PI's discretion.

*Any blood pressure from baseline exceeding or falling below $\pm 20\%$ of baseline or $\geq 140/90$ will necessitate a pause for evaluation.

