5.3.2.2. Adverse Events

AEs will be coded using the most recent version of the Medical Dictionary for Regulatory Activities (MedDRA).

A treatment emergent adverse event (TEAE) is defined as an event that has onset date on or after the first day of exposure to infusion treatment and on or before the last day of infusion treatment. Here the first day of exposure is defined as the first day of exposure to infusion treatment.

Treatment Adverse events (TAES) are summarised descriptively, whereas non-TEAEs are presented in listings. TAE data will be displayed in terms of the number of subjects with at least one event (N), percentage of subjects with at least one event (%) and the number of events (E).

Summaries of TAEs and of serious AEs will be presented as an overview including all AEs, serious AEs, AEs by severity, AEs by relation to treatment, action to AEs and treatment advised, and outcome of AEs.

Furthermore, summary tables based on system organ class and preferred terms are made for:

- All TAEs
- Serious AEs

Hope Biosciences Research Foundation HBPCOVID02

• AEs leading to withdrawal of study

Incidence and risk of AEs of special interest (includes serious or nonserious), including thromboembolic events, infections, and hypersensitivities will be summarized based on system organ class and preferred terms.

Individual adverse events will be listed.

The details of the planned displays are in programming specification document.

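### The treatment-emergent rule works by calendar date only, so a clinically significant finding made before the first infusion at Visit 2 and dated that day is counted as treatment emergent

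*Protocol*

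**What the plan says.** **Treatment emergence.** SAP 5.3.2.2 requires an "onset date on or after the first day of exposure to infusion treatment", and no later than the last infusion day. SAP 7.2.3 makes the day of the first dose Study Day 1, again without a time. SAP 7.2.2 also classifies by date, but its labels are reversed: it gives Y to events before the first dose date and N to events on or after it, or with a missing or partial date. Under SAP 7.2.6, an adverse event with a missing start day in the month of the first dose is set to the first-dose date, unless a complete stop date falls earlier.

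**Visit 2.** The protocol's list for Visit 2 – Infusion 1 (Baseline) puts vital signs at items 2 and 3, examination at item 4, laboratory samples at item 5 and product administration at item 8.

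**What is an adverse event.** Under Physical Examinations, the protocol says: "Pre-existing conditions diagnosed through assessments and examinations at the screening visit or during the screening period are not adverse events". The next sentence covers clinically significant abnormal findings "discovered after informed consent or any pre-existing conditions worsen during the trial, these must be recorded as adverse events". The Vital Signs section also makes clinically significant abnormal results adverse events and exempts no visit.

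**When collection starts.** The Adverse Event Reporting Period section describes "the period from the initiation of any study procedures to the end of the study treatment follow-up". In Table 1 the row "AE and SAE assessments" is marked only from Visit 2, and the Visit 1 procedure list has no adverse event step.

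**The concern.** The incidence of treatment-emergent adverse events is a primary safety endpoint. Its purpose is to count what happens once product has been given. A rule that sees only the date cannot tell a raised blood pressure recorded before the Visit 2 infusion from one that appears an hour after it began. The first cannot have been caused by the product, yet both enter the same table.

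Randomization precedes Visit 2, but the infusion has not begun when these checks are made. The extra events should therefore fall equally on both arms. They add background, which raises both incidences and makes a real excess in one arm slightly harder to see. If the form records no time or flag, the two kinds of event may not be separable at analysis.

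**Working it through.** The plan states no figure on this point, so the check is to apply its rules to example dates and then size the effect under stated assumptions.

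**Step 1: which adverse event rule governs Visit 2?** The exemption names the screening visit and the screening period. Visit 2 is the baseline infusion visit at Week 0 and, on a plain reading, lies outside both. A clinically significant finding there comes after consent, so only the rule that requires recording applies.

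**Step 2: apply the date rules.**

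| Case | Onset date | SAP 5.3.2.2 | SAP 7.2.2 as printed | SAP 7.2.2, labels swapped |
|---|---|---|---|---|
| A. Screening finding | Day −14 | no | Y | N |
| B. Seen before infusion at Visit 2, earlier onset recorded | Day −3 | no | Y | N |
| C. Seen before infusion at Visit 2, dated that day | Study Day 1 | yes | N | Y |
| D. Begins after the infusion, same day | Study Day 1 | yes | N | Y |

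C and D receive the same answer in every column. Correcting the labels in 7.2.2 does not separate them, because the corrected rule is still by date. Case B shows that the onset date decides, not the date of discovery.

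**Step 3: imputed dates.** Take an event that began before the infusion in the same calendar month, has no recorded start day, and has no complete stop date earlier than the infusion. SAP 7.2.6 moves it to Study Day 1, and 5.3.2.2 then counts it.

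**Step 4: effect on the contrast.** Let p be the true treatment-emergent risk in an arm and q the share of participants with a pre-infusion finding dated to Study Day 1. Assume q is equal in both arms and independent of later events.

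- Counted risk = p + q(1 − p)
- Counted risk difference = (1 − q)(p₁ − p₀)

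The documents give neither p nor q. With assumed p₁ = 30% and p₀ = 20%, and 40 per arm (80 participants randomized 1:1):

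| q | Participants of 80 with such a finding | Counted risks | Risk difference | Risk ratio |
|---|---|---|---|---|
| 0 | 0 | 30.0% vs 20.0% | 10.0 points | 1.50 |
| 5% | 4 | 33.5% vs 24.0% | 9.5 points | 1.40 |
| 10% | 8 | 37.0% vs 28.0% | 9.0 points | 1.32 |
| 20% | 16 | 44.0% vs 36.0% | 8.0 points | 1.22 |

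For example, at q = 5%: 0.30 + 0.05 × 0.70 = 0.335; 0.20 + 0.05 × 0.80 = 0.240; difference 0.095 = 0.95 × 0.10.

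**The case against.** **The number of such findings may be small.** Screening excludes listed and investigator-judged laboratory abnormalities and high blood pressure within the preceding 28 days or so. A participant who fails the Visit 2 vital-sign limits is not infused that day, so that day is not the first exposure day. This stands, and it is why no value of q can be defended from the documents. It does not close the gap. The Visit 2 list sets limits for vital signs only, not for laboratory results. Screening requires blood pressure below 140/90, while the Visit 2 limits admit a systolic value up to 160 and a diastolic value up to 95. A finding can thus be judged significant on a day when the infusion proceeds.

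**Onset, not discovery, decides.** This is correct. It would be wrong to infer that every abnormality present at baseline becomes treatment emergent. The problem is confined to onsets entered as, or imputed to, the infusion date.

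**The analysis is descriptive.** SAP 5.3.2.2 reports numbers, percentages and event counts, and defines no risk ratio. It also tabulates events by relation to treatment and lists them individually. This stands too. A low comparator risk makes the ratio look dramatic: at an assumed 20% vs 5%, it falls from 4.0 to 2.46 at q = 5%. On the difference scale, the same case moves only from 15 to 14.25 points. The documents do not support a claim that a large safety signal would be hidden.

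**Does the protocol contradict itself for everything found between consent and first infusion?** A reader might infer this, because consent comes first ("Signing Informed Consent Form (before any trial-related activities"; "After informed consent has been obtained, laboratory samples will be drawn by venipuncture"), and might blame that conflict for the treatment-emergent count. The text supports neither step. The exemption is limited to pre-existing conditions found in screening, so a new finding falls only under the recording rule. The overlap is a pre-existing condition first seen as clinically significant at screening. Even that can be read as history unless new or worse, which fits the protocol's Adverse Event definition. An onset before Study Day 1 is not treatment emergent under 5.3.2.2, so this ambiguity does not feed the count.

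**Conclusion.** The point holds in a limited form. As SAP 5.3.2.2 is written, a clinically significant finding made before the first infusion at Visit 2, with onset dated or imputed to that day, is counted as treatment emergent. Swapping the labels in 7.2.2 would not change this.

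The misclassification should be non-differential. It favours neither arm, inflates incidence in both, and shrinks the risk difference by the factor 1 − q under independence. If the findings fell only on participants with no later event, both incidences would rise by q and the difference would not change. If they fell only on participants who had a later event anyway, the number of participants with an event would not change at all. The size is unknown because the documents give no rate.

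The conclusion rests on reading Visit 2 as outside the screening period, and on onset being entered as the visit date for at least some findings. The second is likely for a vital sign or laboratory value with no symptom history, but the documents do not say so. The change is still worth making: the endpoint is primary for safety, the misclassification follows from a stated rule, and the remedy is cheap.

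**What to change.** **SAP 5.3.2.2, and 7.2.2 once its reversed Y/N labels are corrected.** Count a Study Day 1 event as treatment emergent only if it began or worsened after the start of the first infusion. Take this from an onset time or a pre/post-infusion flag on the adverse event form. If the timing is unknown, including a start date imputed to Study Day 1 with no flag, treat the event as treatment emergent, so that doubt does not remove events from the safety count.

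**Cost.** One extra data field for Study Day 1 events, and matching wording in the two SAP sections.

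**Separately, and as a minor point,** reconcile the protocol's Physical Examinations, Vital Signs, Adverse Event and Adverse Event Reporting Period sections with Table 1. They should agree on when collection starts and on which sentence governs a pre-existing condition first found as clinically significant at screening. This should not send everything before the infusion to medical history. A new illness arising between consent and first infusion is an adverse event under the protocol's definition and reporting period, and removing it would also change what the study stopping rules see.
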